5.1.3 Imputation for MSKCC risk group and IMDC risk group

If any of the following 3 factors are missing the rule below will be used for assign the MSKCC risk group.

1. Karnofsky performance status (< 80%)
2. Low serum hemoglobin (≤ 13 g/dL for males and < 11.5 g/dL for females)
3. High corrected serum calcium (≥ 10 mg/dL)

Number of missing factor(s)	Response from non-missing factor(s) [Yes => patient met the criteria]	Risk group
0	As collected in data base	Use protocol define criteria
1	2 Yes	Poor
1	1 Yes and 1 No	Missing
1	2 No	Missing
2	1 Yes	Missing
2	1 No	Missing
3	NA	Missing

If any of the following 6 factors are missing the rule below will be used for assign the IDMC risk group.

1. Haemoglobin <LLN,
2. Platelet >ULN,
3. Neutrophil >ULN,
4. Corrected serum calcium >ULN,
5. Karnofsky performance status [KPS] <80 and
6. <1 year from diagnosis to first-line targeted therapy

Number of missing factor(s)	Response from non-missing factor(s) [Yes => patient met the criteria]	Risk group
0	As collected in data base	
· If the patient has 0 factor : Favorable prognosis· If the patient has 1-2 factors : Intermediate prognosis· If the patient has 3-6 factors : Poor prognosis
5 factors missing	1 or 0 Yes	Missing
4 factors missing	2, 1 or 0 Yes	Missing
3 factors missing	2, 1 or 0 Yes	Missing
3 factors missing	3 Yes	Poor
2 factor missing	≥ 3 Yes	Poor
2 factor missing	2, 1 or 0 Yes	Missing
1 factor missing	≥ 3 Yes	Poor
1 factor missing	2 Yes	Missing
1 factor missing	1 Yes	Intermediate
1 factor missing	0 Yes	Missing

5.1.4 Other imputations

Incomplete date of initial diagnosis of cancer and date of most recent recurrence

Missing day is defaulted to the 15th of the month and missing month and day is defaulted to 01-Jan.

Incomplete assessment dates for tumor assessment

All investigation dates (e.g. MRI scan, CT scan) must be completed with day, month and year. If one or more assessment dates are incomplete but other investigation dates are available, this/these incomplete date(s) are not considered for calculation of the assessment date and assessment date is calculated as the latest of all investigation dates (e.g. MRI scan, CT scan) if

the overall response at that assessment is CR/PR/SD/UNK. Otherwise – if overall response is progression – the assessment date is calculated as the earliest date of all investigation dates at that evaluation number. If all measurement dates have no day recorded, the 1st of the month is used. If the month is not completed, for any of the investigations, the respective assessment will be considered to be at the date which is exactly between previous and following assessment. If a previous and following assessment is not available, this assessment will not be used for any calculation.

Applying the cut-off to tumor assessment

For tumor related assessments, if an evaluation has some assessments done prior to cut-off date and others after the cut-off date, then the evaluation is considered post-cut-off date and will be excluded from analysis.

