2.2.1 Subgroup of interest

The primary efficacy will be summarized by the following subgroups to examine the homogeneity of treatment effect based on the FAS:

- Age category (< 65 years, ≥ 65 years)

- MSKCC risk groups: poor (≥ 2 risk factors), intermediate (1risk factors), favorable (0 risk factor)
- IMDC risk groups: poor (> 2 risk factors), intermediate (1-2 risk factors), favorable (0 risk factor)
- Line of therapy (2nd / 3rd):
 - Second-Line therapy: all patients who received only one line of prior antineoplastic therapy before start of the study treatment
 - Third-Line therapy: all patients who received two lines of prior antineoplastic therapies before start of the study treatment

No formal statistical test of hypotheses will be performed for the subgroups, only point estimate of the treatment effect and 95% confidence intervals will be provided (see Sections [2.5.4](#) and [2.7.1](#) for further analysis details). The objective of the efficacy subgroup analysis is to evaluate homogeneity of treatment effect in the above subgroups.

Summary tables will only be performed if at least 20% of patients are present in each subgroup. Some grouping of classes may be considered for some subgroups (e.g. therapy type).

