2.3 Patient disposition, demographics and other baseline characteristics

The Full Analysis Set (FAS) will be used for all baseline and demographic summaries and listings unless otherwise specified.

Basic demographic and background data

All demographic and baseline disease characteristics data will be summarized and listed. Categorical data (e.g. gender, age groups: < 65 and ≥ 65 years, race, ethnicity, Karnofsky performance status, MSKCC, IMDC risk group etc.) will be summarized by frequency counts and percentages; the number and percentage of patients with missing data will be provided. Continuous data (e.g. age, weight, height, body mass index etc.) will be summarized by descriptive statistics (N, mean, median, standard deviation, minimum and maximum, 25th and 75th percentiles). BMI (kg/m²) will be calculated as weight[kg] / (height[m]²) using weight at Baseline.

Baseline stratification factors

Not applicable.

Diagnosis and extent of cancer

Summary statistics will be tabulated for diagnosis and extent of cancer. This analysis will include the following: details of tumor histology/cytology, histological grade, stage at initial diagnosis, time since initial diagnosis, stage at time of study entry, presence/absence of target

and non-target lesions, metastatic sites involved. Note: Presence/absence of target and non-target lesions will be based on the data collected on RECIST target/non-target lesion assessment eCRF pages. Presence/absence of metastatic sites will be based on diagnosis page.

Medical history

Medical history and ongoing conditions, including cancer-related conditions and symptoms entered on (e) CRF will be summarized and listed. Separate summaries will be presented for ongoing and historical medical conditions. The summaries will be presented by primary system organ class (SOC) and preferred term (PT). Medical history and current medical conditions will be coded using the Medical Dictionary for Regulatory Activities (MedDRA) terminology. The MedDRA version used for reporting will be specified in the CSR and as a footnote in the applicable tables/listings.

Other

Other data collected at baseline including child bearing potential will be listed.

Patient disposition

The number (%) of treated patients included in the FAS will be presented. The number (%) of patients in the FAS who are still on treatment, who discontinued the study phases and the reason for discontinuation will be presented.

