5.1.2 AE, ConMeds and safety assessment date imputation

Table 5-1 Imputation of start dates (AE, CM) and assessments (LB, EG, VS)

Missing Element	Rule
day, month, and year	
• No imputation will be done for completely missing dates
day, month	
• If available year = year of study treatment start date then
◦ If stop date contains a full date and stop date is earlier than study treatment start date then set start date = 01JanYYYY
◦ Else set start date = study treatment start date.• If available year > year of study treatment start date then 01JanYYYY• If available year < year of study treatment start date then 01JulYYYY
day	
• If available month and year = month and year of study treatment start date then
◦ If stop date contains a full date and stop date is earlier than study treatment start date then set start date= 01MONYYYY.
◦ Else set start date = study treatment start date.• If available month and year > month and year of study treatment start date then 01MONYYYY• If available month and year < month year of study treatment start date then 15MONYYYY

Table 5-2 Imputation of end dates (AE, CM)

Missing Element	Rule (*=last treatment date plus 30 days not > (death date, cut-off date, withdrawal of consent date))
day, month, and year	
• Completely missing end dates (incl. ongoing events) will be imputed by the end date of the on-treatment period*
day, month	
• If partial end date contains year only, set end date = earliest of 31DecYYYY or end date of the on-treatment period *
day	
• If partial end date contains month and year, set end date = earliest of last day of the month or end date of the on-treatment period*

Any AEs and ConMeds with partial/missing dates will be displayed as such in the data listings.

Any AEs and ConMeds which are continuing as per data cut-off will be shown as 'ongoing' rather than the end date provided.

The above imputations are only used for analyses of time to and duration of AEs and concomitant medications.

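### SAP 5.1.4 sets year-only diagnosis dates to 1 January, overstating time since diagnosis by about 6 months on average for those patients; the SAP does not say whether such dates also feed IMDC factor 6

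*SAP*

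**What the plan says.** SAP 5.1.4 has one rule for two dates, headed "Incomplete date of initial diagnosis of cancer and date of most recent recurrence". A date lacking only the day goes to the 15th, so to mid-month. For a date lacking both month and day the rule is "missing month and day is defaulted to 01-Jan", the start of the year.

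SAP 2.3 uses the diagnosis date in the baseline table on extent of cancer, which includes "stage at initial diagnosis, time since initial diagnosis, stage at time of study entry".

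SAP 5.1.3 lists as the sixth IMDC factor "<1 year from diagnosis to first-line targeted therapy". It has its own table for incomplete factors, introduced by "If any of the following 6 factors are missing the rule below will be used for assign the IDMC risk group". With one factor missing, the table gives Missing for 0 or 2 Yes answers, Intermediate for 1, and Poor for 3 or more. SAP 2.2.1 uses IMDC groups (0, 1 to 2, more than 2 factors) as a descriptive PFS subgroup without tests.

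For adverse-event and medication start dates, and for safety assessment dates, Table 5-1 in SAP 5.1.2 has a mid-year branch: "If available year < year of study treatment start date then 01JulYYYY".

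**The concern.** The two halves of the 5.1.4 rule behave differently. The 15th is close to the middle of the month, so its errors nearly cancel. 1 January is the limit of the possible range, so its errors all run one way: the diagnosis is never placed too late, and any interval starting from it is never too short. Time since initial diagnosis is reported directly from this date.

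The second question is IMDC factor 6, which also starts at diagnosis. Protocol 7.1.1.3 lists an MSKCC score, the cancer diagnosis and prior therapies among the screening data, but no IMDC score. A programmer might therefore derive factor 6 from the dates and apply 5.1.4 to the incomplete ones. Another might call the factor missing and go to the 5.1.3 table. The SAP allows both, and they can put the same patient in different IMDC groups.

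**Working it through.** The plan states no figure for this error, so there is none to reproduce. The check enumerates days, assuming the true diagnosis day is uniform over the known year Y. SAP 2.1.1 gives a month as 30.4375 days and a year as 365.25 days.

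**1. Time since diagnosis, month and day missing.** Error = true date minus imputed date; a positive value overstates the interval.

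- 1 January: mean (0 + 1 + … + 364)/365 = 182 days; 182/30.4375 = 5.98 months. In a leap year, 182.5/30.4375 = 6.00 months. Range 0 to 364/30.4375 = 11.96 months.
- 1 July (day 181 counted from 1 January as day 0): mean 182 − 181 = 1 day, or 0.03 months. Range −181/30.4375 = −5.9 to 183/30.4375 = +6.0 months.
- If the interval ends in year Y itself, later diagnosis dates are ruled out. The mean overstatement under 1 January falls to about 3 to 4 months, depending on how the two dates are weighted.
- Day only missing, set to the 15th: mean error 0.7 day.

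**2. IMDC factor 6, if the imputed date is used.** First-line targeted therapy is taken as uniform within a calendar year (a further assumption).

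- Therapy in year Y: the interval is always under 1 year, and imputation does not change that. No errors.
- Therapy in Y+2 or later: the interval always exceeds 1 year. No errors.
- Therapy in Y+1: with diagnosis D uniform on (0, 1) and therapy T uniform on (1, 2), P(T − D < 1) = 0.50. Setting D = 0 gives T − D ≥ 1 throughout, so no patient is classed as under 1 year. By days, 49.9% go from Yes to No and 0% from No to Yes. With 1 July, 12.6% go from Yes to No and 12.4% from No to Yes: balanced, but still about 25% wrong.

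**3. Effect on the IMDC group when factor 6 is truly Yes.**

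| Other five factors, total | True group | Factor 6 falsely No | Factor 6 missing (5.1.3) |
|---|---|---|---|
| 0 | Intermediate | Favorable | Missing |
| 1 | Intermediate | Intermediate | Intermediate |
| 2 | Poor | Intermediate | Missing |
| 3 to 5 | Poor | Poor | Poor |

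The group changes only at totals of 0 and 2. If the factor is treated as missing, nobody moves to a better group.

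**4. Scale.** The documents do not give the share of year-only dates. Assume 1% to 10%, with 10% to 50% of those patients starting first-line therapy in Y+1. Wrong factor 6 values per 100 patients then run from 100 × 0.01 × 0.10 × 0.5 = 0.05 to 100 × 0.10 × 0.50 × 0.5 = 2.5. Fewer than that change group.

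**The case against.** The strongest objection concerns IMDC. A reader might infer from 5.1.4 that the trial's IMDC groups are shifted toward better risk. The documents do not support that. Nothing links the imputed date to factor 6, and the table in 5.1.3 may apply instead, in which case nobody moves to a better group. Factor 6 also ends at first-line targeted therapy. Inclusion criterion 5 admits patients whose only prior line was a checkpoint inhibitor alone, and the SAP does not say which date closes the interval for them. This objection stands: the IMDC effect is conditional, and step 2 rests on an assumed interval.

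A reader might also infer that time since diagnosis is overstated by 6 months across the trial. It is not. Only dates lacking both month and day are affected, and that set may be empty.

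Nor does Table 5-1 make 5.1.4 self-contradictory. SAP 5.1.2 confines its rules to time to, and duration of, adverse events and concomitant medications, and two other year-only branches of that table use 1 January. The table shows only that a mid-year default is already in use for an earlier year. The better comparison is the mid-month rule in the same sentence of 5.1.4.

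Finally, 1 January cannot fall after a treatment given in the diagnosis year, whereas 1 July can. This is correct, and the replacement needs a bound.

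None of this removes the one-way error in the reported time since initial diagnosis, which does not depend on the IMDC link.

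**Conclusion.** The point holds in limited form, as a minor one. For diagnosis dates known only to the year, the 1 January default overstates time since initial diagnosis by about 6 months on average. That size assumes dates uniform over the year; the direction needs no such assumption.

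For IMDC, the finding is a gap in the SAP together with a conditional risk. If the imputed date feeds factor 6, every error sets the adverse factor to No. This needs first-line targeted therapy in the calendar year after diagnosis (about 50% wrong there under uniform dates), and a group change also needs exactly 0 or 2 other factors.

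The consequences stay within a baseline summary and, possibly, descriptive subgroup tables. The primary PFS estimate, OS, ORR and the sample size do not depend on this rule. The same default for the most recent recurrence date shows no harm, because SAP 2.3 lists no summary that uses that date.

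**What to change.** In SAP 5.1.4, impute a year-only date of initial diagnosis as 1 July of that year, or as the date of the first recorded anticancer therapy or surgery if that is earlier. Leave the recurrence-date rule as it is.

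For IMDC factor 6, add to SAP 5.1.3 that the factor is set to Yes or No only when every date in the known year gives the same answer, and is otherwise missing and handled by the existing table. Therapy in the diagnosis year then gives Yes, therapy two or more calendar years later gives No, and therapy in the year between is generally missing. Mid-year imputation alone would not be enough for this factor, since it still misclassifies about 25% in that window.

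The cost is a sentence in each section, one bounding rule in the derivation, and possibly a few more Missing IMDC groups. Where the bound applies, the imputed date is the latest one possible and the error runs the other way, by at most 181 days (181/30.4375 = 5.9 months). No new data are needed. SAP 2.2.1 produces subgroup tables only if each subgroup holds at least 20% of patients, so extra Missing values would matter only for a group close to that limit.

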5.2 AEs coding/grading

Adverse events are coded using the Medical dictionary for regulatory activities (MedDRA) terminology.

Note: The latest available MedDRA version at the time of the analyses should be used. The MedDRA version used should be specified in the footnote of relevant tables.

AEs will be assessed according to the Common Terminology Criteria for Adverse Events (CTCAE) version 4.03.

The CTCAE represents a comprehensive grading system for reporting the acute and late effects of cancer treatments. CTCAE grading is by definition a 5-point scale generally corresponding to mild, moderate, severe, life threatening, and death. This grading system inherently places a value on the importance of an event, although there is not necessarily proportionality among grades (a grade 2 is not necessarily twice as bad as a grade 1).

5.3 Laboratory parameters derivations

Grade categorization of lab values will be assigned programmatically as per NCI Common Terminology Criteria for Adverse Events (CTCAE) version 4.03 (specify version used in the RAP). The calculation of CTCAE grades will be based on the observed laboratory values only, clinical assessments will not be taken into account. The criteria to assign CTCAE grades are given in Novartis internal criteria for CTCAE grading of laboratory parameters. The latest available version of the document based on the underlying CTCAE version 4.03 at the time of analysis will be used. For laboratory tests where grades are not defined by CTCAE v4.03, results will be graded by the low/normal/high classifications based on laboratory normal ranges.

A severity grade of 0 will be assigned for all non-missing lab values not graded as 1 or higher. Grade 5 will not be used. For laboratory tests that are graded for both low and high values, summaries will be done separately and labelled by direction, e.g., sodium will be summarized as hyponatremia and hypernatremia.

Imputation Rules

CTC grading for blood differentials is based on absolute values. However, this data may not be reported as absolute counts but rather as percentage of WBC.

If laboratory values are provided as '<X' (i.e. below limit of detection) or '>X', prior to conversion of laboratory values to SI unit, these numeric values are set to X.

The following rules will be applied to derive the WBC differential counts when only percentages are available for a xxx differential

$$\text{xxx count} = (\text{WBC count}) * (\text{xxx \%value} / 100)$$

Further derivation of laboratory parameters might be required for CTCAE grading. For instance, corrected calcium can be derived using the reported total calcium value and albumin at the same assessment using the following formula:

$$\text{Corrected Calcium (mg/dL)} = \text{Calcium (mg/dL)} - 0.8 [\text{Albumin (g/dL)} - 4]$$

In order to apply the above formula, albumin values in g/L will be converted to g/dL by multiplying by 0.1), calcium values in mmol/L will be converted to mg/dL by dividing by 0.2495. For calculation of laboratory CTC grades 0 and 1, the normal range for derived corrected calcium is set to the same limits (in mg/dL) as for calcium.

CTC grades for the derived absolute WBC differential counts (neutrophils, lymphocytes) and corrected calcium will be assigned as described above for grading

5.4 Statistical models

5.4.1 Primary analysis

Analysis of time to events Data

Hypothesis and test statistic

Not applicable.

Kaplan-Meier estimates

An estimate of the survival function in each treatment group will be constructed using Kaplan-Meier (product-limit) method as implemented in PROC LIFETEST with METHOD=KM option. The PROC LIFETEST statement will use the option CONFTYPE=LOGLOG.

Median survival for each treatment group will be obtained along with 95% confidence intervals calculated from PROC LIFETEST output using the method of [\[Brookmeyer and Crowley 1982\]](#). Kaplan-Meier estimates of the survival function with 95% confidence intervals at specific time points will be summarized. The standard error of the Kaplan-Meier estimate will be calculated using Greenwood's formula [\[Collett 1994\]](#).

Treatment of ties

The STRATA statement in LIFETEST procedure will be used to analyze time to event data with ties.

Analysis of Binary Data

Single arm study

Confidence interval for response rate

Responses will be summarized in terms of percentage rates with $100(1 - \alpha)\%$ confidence interval using exact binomial confidence interval (implemented using SAS procedure FREQ with EXACT statement for one-way table [Clopper and Pearson 1934]).

Multiplicity adjustment

Not applicable.

Key secondary analysis

Not applicable.

6 Reference

1. Brookmeyer R and Crowley J (1982). A Confidence Interval for the Median Survival Time. *Biometrics*, 38, 29 - 41.
2. Celli, et al (2007) Development and Validation of a Scale to Measure Disease-Related Symptoms of Kidney Cancer. *Value in Health*; Vol. 10
3. Clopper CJ and Pearson ES (1934). The use of confidence or fiducial limits illustrated in the case of the binomial. *Biometrical*, 26, 404-413.
4. Collet D (1994). Modelling survival data in medical research. London, Chapman & Hall.
5. FDA briefing Document Oncologic Drugs Advisory Committee Meeting, July 24, 2012, Evaluation of radiologic review of progression-free survival in Non-hematologic malignancies.
<http://www.fda.gov/downloads/advisorycommittees/committeesmeetingmaterials/drugs/oncologicdrugsadvisorycommittee/ucm311141.pdf>
6. Nadal, et al (2016) Safety and clinical activity of vascular endothelial growth factor receptor (VEGFR)-tyrosine kinase inhibitors after programmed cell death 1 inhibitor treatment in patients with metastatic clear cell renal cell carcinoma. *Annals of Oncology* 27:1304-1311
